6.9.2. Collection of Oral Mucosa

Oral mucosa will be collected before the first dose of the study drug and stored frozen (-20°C or below) until transportation. The investigator or subinvestigator will record the date of collection in the case report form. The specimens should be managed by attaching a code unrelated to the subjects to avoid leaking of subjects' personal information.

6.9.3. Storage Period

The storage period of the banking specimens will be up to a maximum of 15 years after the day of submission of the clinical trial plan notification.

6.9.4. Disclosure of Results of Genome/Gene Analysis Using Banking Specimens

The timing, methods, accuracy of the results, and clinical significance of the genome/gene analysis using banked specimens remain unknown at present. In this context, disclosure of the results of genome/gene analysis to investigators and subjects is not planned.

6.9.5. Disposal of Banking Specimens

After the expiration of the storage period or at the time of a subject's withdrawal of consent during the storage period, the banking specimens will be disposed of without delay. If the gene analysis has been performed before the expiration of the storage period or before the subject's withdrawal of consent, the data will not be destroyed.

7. PHARMACOKINETIC ENDPOINTS

The pharmacokinetic parameters listed below will be calculated from plasma concentrations of DS-3032a using the non-compartmental analysis.

Pharmacokinetic parameters (Subtrial A):

C1D1 (Cycle 1 Day 1): Cmax, Tmax, AUClast, AUC8h, AUC24h, AUCinf*, Kel*, t1/2*, CL/F*, Vz/F*

C1D14 (Cycle 1 Day 14)**: Cmax, Ctrough, Cavg, Tmax, AUC8h, AUC24h, Kel*, t1/2*, CLss/F***, Vz/F****, AR

*: To be calculated only if possible.

**: To be read as C1D7 (Cycle 1 Day 7) in Subtrial B, C1D3 (Cycle 1 Day 3) in Subtrial C, and C1D15 (Day 15) in Subtrial D.

***: Not to be calculated because steady state will not be reached in Subtrial C.

The details of the method of calculation of pharmacokinetic parameters are specified in the Statistical Analysis Plan.

Rationale:

To evaluate the pharmacokinetics of DS-3032b administered as a single dose or multiple doses, general pharmacokinetic parameters after oral dosing are selected.

8. PHARMACODYNAMIC ENDPOINTS

The following pharmacodynamic parameters will be analyzed:

- *TP53* mutation
- Serum MIC-1 level

Rationale:

These pharmacodynamic parameters that can be drug-related markers will be measured to assess the pharmacological or clinical effect of DS-3032b in each individual.

9. SAFETY ENDPOINTS

Safety endpoints will be AEs, ECOG PS, laboratory data, body weight, vital signs, and 12-lead ECG.

9.1. Definition of Adverse Events

An AE is any untoward or unintended sign (including an abnormal change in laboratory data or vital signs), symptom, or disease noted in subjects who received the study drug, whether it is considered to be related to the study drug or not.

A symptom or disease preexisting before the start of study treatment will be handled as a complication, not as an AE. However, complications that have worsened during the study treatment will be handled as AEs, and the date when worsening is confirmed will be used as the date of onset of the relevant event.

It is the responsibility of investigators, based on their knowledge and experience, to determine those circumstances or abnormal laboratory data which should be considered as AEs.

Progression of the primary disease (AML) will be handled as follows:

- Tumor progression will not be considered as an AE. However, if tumor progression results in death during the AE collection period, it will be handled as an SAE (this should be recorded as “disease progression” for the event term and “fatal” for the outcome).
- Worsening of signs or symptoms resulting from tumor progression will be handled as AEs.

9.2. Definition of Serious Adverse Events

An SAE is any AE that:

- results in death,
- is life-threatening,
- requires inpatient hospitalization or prolongation of existing hospitalization for treatment,
- is a disability or incapacity,
- may lead to a disability or incapacity,
- represents other medically important condition, or
- is a congenital anomaly or birth defect.

SAEs that occurs after the informed consent will be collected.

9.3. Adverse Event Information to be Reported

If an AE occurs during the study, the items shown in “[Table 9.3.1 Adverse Event Information to be Reported](#)” will be investigated and recorded in the case report form. If a medical interview is used to investigate symptoms, questions that specify symptoms should not be used. If a subject has two or more signs (including symptoms and abnormal changes in laboratory data) that are correlated with each other and can be considered part of one diagnosis, they will be regarded as one single event, and the diagnosis will be recorded as an AE in the case report form. Only the highest grade observed in the course of each AE should be recorded as the severity in the case report form.

AEs will be graded according to the “CTCAE Version 5.0.” AEs that are not listed in the CTCAE Version 5.0 will be graded according to the definitions provided in “[Table 9.3.1 Adverse Event Information to be Reported](#).”

Table 9.3.1: Adverse Event Information to be Reported

Item	Details to be Assessed		
AE	Name of AE, date of onset		
Action taken for AE	Whether or not action was taken (including the modification of administration of the study drug), and if taken, details of the action.		
Outcome	Outcome category, date of outcome assessment, date of resolution		
	Outcome category	
Recovered/ Resolved
 
Recovering/ Resolving
 
Not recovered/ Not resolved
 
Recovered/ Resolved with sequelae/ residual effect(s) present
 
Fatal
 
Unknown
	
The AE has resolved, and the subject has recovered to the pre-event condition.
 
The AE has almost resolved, and the subject has nearly recovered to the pre-event condition.
 
The AE has not resolved, and the condition of the subject is similar to that at onset (unchanged).
 
The AE has resolved, but the subject has sequelae.
 
Tumor progression will not be handled as an AE. However, tumor progression leading to a fatal outcome during the AE collection period should be handled as a SAE (with the name and outcome of the event recorded as “disease progression” and “fatal,” respectively).
 
Outcome is unknown because of lack of information.

Severity	
To be assessed according to the CTCAE Version 5.0.
 
The severity of AEs not included in the CTCAE Version 5.0 will be assessed according to the following grades:
 
Grade 1 Mild; asymptomatic or mild symptoms; clinical or diagnostic observations only; intervention not indicated.
 
Grade 2 Moderate; minimal, local or noninvasive intervention indicated; limiting age-appropriate instrumental activities of daily living (ADL).
 
Grade 3 Severe or medically significant but not immediately life-threatening; hospitalization or prolongation of hospitalization indicated; disabling; limiting self care ADL.
 
Grade 4 Life-threatening consequences; urgent intervention indicated.
 
Grade 5 Death related to AE.
		
Seriousness	Serious/Nonserious		
Causality with the study drug	Classification of the relationship (in accordance with the following classification of the relationship), reason for the assessment		
	Causality category	
Related
 
 There is a reasonable temporal relationship between the onset of the adverse event and administration of the study drug, it is not reasonable to assess that the adverse event is attributable to the subject’s condition or other factors than the study drug (underlying disease, complications, concomitant drugs, etc.), and a relationship with the study drug cannot be ruled out. There is a reasonable temporal relationship between the onset of the adverse event and administration of the study drug, and the adverse event can be explained by known actions or the pharmacological action of the study drug or similar analogues. 
Unrelated
 
 There is no reasonable temporal relationship between the onset of the AE and administration of the study drug, it is reasonable to assess that the AE is attributable to the subject’s condition or other factors than the study drug (underlying disease, complications, concomitant drugs, etc.), and a relationship with the study drug can be ruled out. 	

9.4. Definition of Adverse Drug Reactions

AEs that are assessed as “related” to the study drug will be handled as adverse drug reactions.

9.5. Actions to be Taken for Adverse Events

9.5.1. Recommended Action for Adverse Events

If any adverse event has occurred, the investigator or subinvestigator will provide appropriate medication, notify the sponsor as required, and continue follow-up until the subject recovers to the pre-event condition with resolution or relief of the adverse event as far as possible, even after the end of this study. However, even if the adverse event is not confirmed to have resolved or relieved, if it is judged that the subject’s condition remains stable and the safety can be assured, the investigator or subinvestigator will explain the matter to the subject, and the follow-up of the study will be completed (treatment of the relevant symptom will be continued).

9.5.2. Action for Serious Adverse Events

If an SAE has occurred, the investigator or subinvestigator will provide appropriate medication, and report the details of the SAE to the sponsor by telephone or fax within 24 hours of learning of the occurrence. The investigator will also record the necessary information in the “Serious Adverse Event Report (SAVER)” Form, sign it with the date of confirmation, and immediately report it to the sponsor. A written report to the head of the study center will be made in accordance with the procedures and format specified by the study center.

9.6. Actions to be Taken in the Event That Information on Pregnancy, Pregnant and Parturient Women, and Delivery is Obtained

If information on the pregnancy of a subject or a subject’s female partner is obtained during the study period or within 95 days after the last dose of the study drug, the investigator or subinvestigator will investigate the information on the pregnancy through delivery, and report it to the sponsor using the format provided by the sponsor.

Pregnancy will not be handled as an AE; however, if the outcome of the pregnant woman falls under the definition of SAEs (congenital anomaly in the fetus [including suspected cases], stillbirth, abortion, etc.), the investigator or subinvestigator must report it to the sponsor in accordance with the procedures for reporting SAEs specified in “Section 9.5.2 Action for Serious Adverse Events,” independent of whether it is during the study period or not.

10. EFFICACY ENDPOINTS

The antitumor effect of DS-3032b will be evaluated based on bone marrow findings and peripheral blood results (neutrophil count, platelet count, and number of blasts), as specified in “[Table 10.1.1 Definition of Efficacy Endpoints](#).”

10.1. Definition of Efficacy Endpoints

The response criteria are defined as follows.

Table 10.1.1: Definition of Efficacy Endpoints

Complete remission: CR*	Bone marrow blasts <5%, neutrophil count $\geq 1000 / \text{mm}^3$, and platelet count $\geq 100,000 / \text{mm}^3$ in the absence of RBC or platelet transfusion (4 weeks for RBC transfusion, 1 week for platelet transfusion); absence of Auer rods; absence of extra-medullary leukemia. Absence of peripheral blasts.
CR with incomplete hematological recovery: CRI	All CR criteria are met, except for neutrophil count $< 1000 / \text{mm}^3$ and platelet count $\geq 100,000 / \text{mm}^3$ or neutrophil count $\geq 1000 / \text{mm}^3$ and platelet count $< 100,000 / \text{mm}^3$.
CR with partial hematological recovery: CRh**	All CR criteria are met, except for neutrophil count $> 500 / \text{mm}^3$ and platelet count $> 50,000 / \text{mm}^3$.
Partial remission: PR	Neutrophil count $\geq 1000 / \text{mm}^3$ and platelet count $\geq 100,000 / \text{mm}^3$ in the absence of RBC or platelet transfusion (4 weeks for RBC transfusion, 1 week for platelet transfusion); decrease in bone marrow blast percentage by at least 50% and total bone marrow blast percentage of 5% to 25%.
Morphologic leukemia-free state: MLFS	Bone marrow blasts <5% in the absence of blasts with Auer rods; absence of extra-medullary leukemia. The presence/absence of hematological recovery or blood transfusion is not considered.
Stable disease: SD	Absence of CR, CRI, CRh, PR, or MLFS; and criteria for PD not met.
Progressive disease: PD	When any of the following apply: ≥ 1.5 -fold increase in bone marrow blasts over baseline (eg, increase in blast count from 35% to $> 52.5\%$). At least 15% point increase in bone marrow blasts in cases with <30% blasts at baseline (eg, increase in blast count from 20% to 35%). Persistent bone marrow blast percentage of $> 70\%$ over at least 3 months. Cases with improvement in neutrophil count to $\geq 500 / \text{mm}^3$ and/or improvement in platelet count to $\geq 50,000 / \text{mm}^3$ (without transfusion) are excluded. ≥ 1.5 -fold increase in peripheral blasts (WBC \times % blasts) to $> 25,000 / \text{mm}^3$, in the absence of differentiation syndrome. New extra-medullary leukemia.
Relapse	Relapse after CR, CRI, or CRh (except in case the criteria for MLFS are also met): Either of appearance of peripheral blasts, bone marrow blast percentage $\geq 5\%$, or relapsed or new extra-medullary leukemia.
Unknown	No post-baseline evaluation.

* If a subject meets the criteria for both CR and CRh, the outcome should be captured in the case report form as CR.

** If a subject meets the criteria for both CRI and CRh or for both CRh and MLFS, the outcome should be captured in the case report form as CRh.

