10.2. Best Response

Best response is defined as the best measured response over all response assessments (CR, CRi, CRh, PR, MLFS, SD, or PD) at all time points after the start of study treatment.

The best response will be SD if the response is assessed as SD three or more times consecutively in the protocol-specified evaluation of the antitumor effect. If the response is not assessed as SD three or more times consecutively, the best response will be Not Applicable (unconfirmed SD).

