11.4.3. Efficacy Analysis

The efficacy analyses will be performed on the efficacy analysis set, unless otherwise noted.

For the best response (CR, CRi, CRh, PR, MLFS, SD, and PD), frequency tables will be prepared. The point estimate and the 95% CI will be calculated for the CRc rate, response rate, and transplantation rate (as a subsequent AML treatment).

For the duration of CRc, summary statistics will be calculated using the Kaplan-Meier method.

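### Table 10.1.1: for baseline marrow blasts above 0% and below 30%, the 15-point progression line never decides a case, because the 1.5-fold line has no baseline limit

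*Combined protocol and SAP*

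**What the plan says.** The PD row of Table 10.1.1 (Section 10.1) opens with "When any of the following apply", so one line is enough. Two of its lines concern a rise in marrow blasts.

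- **Fold line:** a 1.5-fold or greater "increase in bone marrow blasts over baseline (eg, increase in blast count from 35% to" more than 52.5%). No baseline range is given.
- **15-point line:** "At least 15% point increase in bone marrow blasts in cases with <30% blasts at baseline", with a rise from 20% to 35% as its example.

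The SD row requires that no remission category applies, "and criteria for PD not met". Section 10.2 gives a best response of SD only after three consecutive SD assessments: "If the response is not assessed as SD three or more times consecutively, the best response will be Not Applicable (unconfirmed SD"). Section 11.4.3 then tabulates the result: "For the best response (CR, CRi, CRh, PR, MLFS, SD, and PD), frequency tables will be prepared".

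**The concern.** A separate line for baselines below 30% should do something there that the general line does not. With the lines joined by any and the fold line open to every baseline, the general line takes over the whole range that the special line was written for. A subject with few blasts at baseline is then scored PD on a rise of a few points, well short of 15.

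At stake is the SD/PD call. SD is defined by the absence of PD and best response SD needs an unbroken run of three. One marrow value between the two thresholds can therefore move a subject from SD to PD, or from SD to unconfirmed SD, in the best-response table.

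**Working it through.** **Inputs.** All come from the PD row of Table 10.1.1. Let b be baseline marrow blasts (%) and p a later value.

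- Fold line: p ≥ 1.5b, any baseline.
- 15-point line: p ≥ b + 15, only if b < 30.
- PD on marrow rise: either line.

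**The plan's own examples.** 35 × 1.5 = 52.5 and 20 + 15 = 35, so both reproduce. The second example is also a 35/20 = 1.75-fold rise, and the fold threshold at that baseline is 20 × 1.5 = 30%. The example meant to show the 15-point line had already reached PD five points earlier.

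**General result.** (b + 15) − 1.5b = 15 − 0.5b. This is above 0 for every b with 0 < b < 30, and equals 0 at b = 30. In that range any p that meets the 15-point line also meets the fold line.

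| Baseline | Fold threshold | 15-point threshold | Gap (points) | Fold rise at 15-point threshold |
|---|---|---|---|---|
| 5% | 7.5% | 20% | 12.5 | 4.0 |
| 6% | 9% | 21% | 12 | 3.5 |
| 10% | 15% | 25% | 10 | 2.5 |
| 15% | 22.5% | 30% | 7.5 | 2.0 |
| 20% | 30% | 35% | 5 | 1.75 |
| 25% | 37.5% | 40% | 2.5 | 1.6 |
| 29% | 43.5% | 44% | 0.5 | 1.52 |
| 30% | 45% | 45% | 0 | 1.5 |

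**Counts, as a check on the algebra.** Take whole-percent baselines 5 to 29% and later values 0 to 100%.

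- The 15-point line is met in Σ(86 − b) = 25 × 86 − 425 = 1,725 pairs. All 1,725 also meet the fold line, so the 15-point line alone decides 0.
- The fold line alone decides Σ floor(15 − 0.5b) = 78 (even b) + 78 (odd b) = 156 pairs.

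On a 0.1-point grid for baselines 0.1 to 29.9%, 209,599 pairs meet the 15-point line and none fails the fold line. Another 22,350 pairs meet the fold line only. The result is the same if the fold line is read as strictly greater than 1.5-fold, as its example is printed. These counts show the logic only, not how many subjects are affected.

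**Alternative reading of the fold line.** If a 1.5-fold increase meant a rise to 2.5b, the 15-point line would decide cases for 10 < b < 30, since 2.5b > b + 15 when b > 10. The printed example excludes this: 2.5 × 35 = 87.5, not 52.5.

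**What can change.** For baselines of 5% or more, every value between the thresholds is at least 7.5% and above baseline. It cannot be CR, CRi, CRh or MLFS (each needs blasts below 5%) or PR (which needs a fall of at least 50%). Only the SD/PD call is open.

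**Illustration, baseline 20%.** Marrow values of 22%, 31% and 28% are ratios of 1.10, 1.55 and 1.40, and rises of 2, 11 and 8 points. As written they score SD, PD, SD, with no run of three. If only the 15-point line governed, they score SD, SD, SD. This holds only if the subject stays under assessment after the PD score.

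**The case against.** The strongest reply is that nothing here is ambiguous. For 0 < b < 30 every marrow value gets one answer, so this is redundancy, not contradiction, and a redundant line harms nobody if the fold line was meant to apply throughout. The first part stands: the table can be applied as printed. The second depends on intent, which the protocol does not state. Three features point the other way: the 15-point line carries an explicit limit of 30%, the fold line's example has a baseline above 30%, and the two thresholds cross at exactly 30%. A reader might infer from this that misdrafting is proved. It is not. The bullets and indents of the PD cell are also lost in the text available, so nesting of one line under the other cannot be excluded, although no words state it.

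Four stronger readings are tempting and are not supported.

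- **The line is dead at every baseline below 30%.** At 0% a fold change is undefined, and Section 4.1.1 sets no minimum marrow blast percentage. There the 15-point line is the only workable marrow-rise test.
- **It changes who is withdrawn.** Section 5.6 lists apparent progression as a withdrawal reason but does not cite Table 10.1.1. The same criterion is why the three-visit illustration is conditional: a subject scored PD at 31% may have no later marrow.
- **It affects the main results.** The antitumor evaluation is exploratory (Section 2), and the analysis is descriptive in a planned 9 to 24 subjects (Section 11.6).
- **The relapse row has a similar defect**, because its exception "except in case the criteria for MLFS are also met" gives no visit. The natural meaning is that MLFS is met at the suspected-relapse visit, together with the relapse criteria. Testing it at remission would cancel every relapse and is not a credible reading.

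Section 11 defers further statistical detail to a separately prepared Statistical Analysis Plan. The documents supplied contain no resolution, and the response definitions themselves sit in the protocol.

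**Conclusion.** The point holds, as a minor one. As written, the 15-point line has no effect for any baseline above 0% and below 30%, and PD is called up to 15 − 0.5b points sooner than that line would call it. That is 12 points at a baseline of 6%, 10 at 10%, 5 at 20% and 0.5 at 29%.

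The algebra is certain, given that the lines are alternatives and that the fold line means 1.5 times baseline; the table's wording and example support both. That the 15-point line was meant to govern below 30% is likely but unproven. The consequence is confined to SD, PD and unconfirmed-SD entries in the best-response table. DLT evaluation, MTD, CRc rate, response rate and transplantation rate do not use PD. The baseline blast distribution is not given, so the number of subjects affected is unknown.

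**What to change.** Before the efficacy analysis, reconcile the two marrow lines by stating the baseline range that each governs. Limit the fold line to baselines of 30% or more, and require the 15-point rise when baseline is below 30%. The thresholds meet at 45% for a 30% baseline, so the rule has no jump there. The PD threshold would move from 9% to 21% at a baseline of 6%, from 15% to 25% at 10%, and from 30% to 35% at 20%.

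If the sponsor did intend the fold line throughout, the table should say so and keep a rule for a 0% baseline. Simply deleting the 15-point line is not a remedy: it changes no result for baselines between 0% and 30%, and it leaves a 0% baseline with no marrow-rise test.

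The cost is a line or two of wording and no new data. The downside of the first option is that PD is called somewhat later in subjects with low baseline blasts. Settling it in advance avoids choosing between the readings once the marrow values are known.

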10.2. Best Response

Best response is defined as the best measured response over all response assessments (CR, CRi, CRh, PR, MLFS, SD, or PD) at all time points after the start of study treatment.

The best response will be SD if the response is assessed as SD three or more times consecutively in the protocol-specified evaluation of the antitumor effect. If the response is not assessed as SD three or more times consecutively, the best response will be Not Applicable (unconfirmed SD).

10.3. Duration of Composite Complete Remission

The duration of composite CR (CRc) is defined as the length of time from the time when the criteria for CRc (CR + CRi + CRh) are first met to the time when a relapse was first confirmed.

11. STATISTICAL ANALYSIS

An outline of the statistical and pharmacokinetic analyses is provided below. Statistical methods will be specified in more details in the separately prepared Statistical Analysis Plan.

